#### *Exclusion Criteria-Patient Participants*

- (1) We will not enroll individuals who are in law enforcement custody at admission to the designated rehabilitation unit or who are taken into custody prior to discharge from the designated rehabilitation unit due to federal restrictions on inclusion of prisoners in research.
- (2) We will not enroll individuals who do not have access to a phone.
- (3) We will not enroll individuals who are unable to complete study procedures due to cognitive/verbal limitations AND do not have a proxy to assist with study procedures.

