The day of clearance of PTA is the first day the person gets the first of 2 consecutive scores of 76 or greater on the GOAT, the first of 2 consecutive scores of 11 or greater on the Revised GOAT, the first of 2 consecutive scores of 25 or greater on the Orientation-Log, or the first of 2 consecutive scores of 8 or greater on the Non-Verbal version of the Orientation-Log.”

As per standard TBIMS procedure, if the patient is deemed oriented, the research staff will introduce the study using a talking points script, and if the potential participant is interested, provide him/her with a brochure and a consent form.

Research staff will initiate the informed consent process if a) the patient is deemed oriented per definition above, and b) the patient expresses interest in participating. Research staff will visit the patient on a subsequent day and re-administer the orientation test prior to consent if needed.

*Patient Unable to Provide Consent*

If the patient is not deemed oriented as per the outline above, the patient is unable at that time to provide informed consent. Research staff may administer the orientation test multiple times to determine capacity to consent.

If patient is unable to provide consent either due to aphasia, non-emergence from PTA, and/or being non-verbal:

1. Staff will determine if patient has a Legally Authorized Representative (LAR) who is willing and available to provide consent as a proxy for the patient:
  - a. If Yes: Staff may enroll the patient participant via proxy- go to #2 below;
  - b. If No: Staff will deem the patient ineligible due to not being able to provide consent/no proxy- stop here.
2. Staff will determine if patient has an individual who is willing and available to assist with both participation in the RTP (if randomized to that arm)\* AND the follow-up questionnaires\*\* for the foreseeable future. Specifically, the individual would need to be present for all potential RTP contacts and questionnaires. This individual does not need to be the same person that provided proxy consent:
  - a. If Yes: Staff may enroll the patient participant via proxy-stop here;
  - b. If No: Staff will consult with trained clinical staff to conclude whether it is more likely than not that the patient participant will be able to participate on his/her own within one month following discharge given nature and degree of severity of limitations:
    - i. If Yes: Staff may enroll the patient participant via proxy;\*\*\*

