    - ii. If No: Staff will deem the patient ineligible due to inability to complete study procedures due to cognitive/verbal limitations AND not having a proxy to assist with study procedures.

\*If the proxy individual is not enrolled as a caregiver participant in the study, the TCM would only engage the proxy individual in resource facilitation and the needs assessment as it specifically pertains to the patient participant. The TCM will not conduct a caregiver needs assessment with the proxy or provide resources that pertain specifically to the proxy individual as they are not enrolled as a caregiver. If the TCM infers that the proxy individual would like to participate in the needs assessments/resource facilitation as it pertains to them (e.g., as the caregiver), the TCM would remind the proxy individual in a non-coercive manner of the opportunity to participate as a caregiver participant. This would require the completion of the informed consent process with the proxy individual as per study protocol.

\*\*In this scenario, the proxy individual would not complete the QOLIBRI as part of the post-discharge questionnaire. In addition, the individual would not complete the following items on the Form II: SWLS, GEN, GNHLTH, PHQ, GAD

\*\*\*Staff will withdraw the patient participant following randomization if the participant is deemed unable to participate due to limitations within the following timeframes:

1. The TCM will withdraw the patient participant one month following discharge if randomized to RTP arm of the study;
2. Blinded staff will withdraw the patient participant three months following discharge if randomized to RDP arm of the study;

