The patient participant may be mailed or emailed a response key along with a cover letter to assist with completing the questionnaires described in the "Follow Up Data Collection" section below.

The patient participant may also be mailed or emailed a log along with a cover letter to assist with keeping track of use of medical services during study participation. Medical services utilization will be assessed as part of the Cornell Services Index described in the "Follow Up Data Collection" section below.

*Patient Participant Incapable of Consent while Inpatient or Directly After (Telephone Approach)*

If the patient is deemed unable to provide consent, consent of a legally authorized representative (LAR) will be sought and a family member or caregiver will be asked to provide verbal consent on the patient's behalf. The caregiver/family member giving assent will be provided with as much time as needed to review the Patient Information Sheet and ask the research staff member questions about the form, the patient's rights as a participant, and participation in the study. The respective party will be fully informed of all risks and benefits prior to giving his/her written informed assent and prior to enrollment in the study.

The individual will then be asked to give verbal consent to participate. Research staff will document receipt of verbal consent per site protocol, as well as update the BRITE website Screening form to indicate consent and enrollment.

*Patient Participant Capable of Consent Following Discharge*

Research staff will re-assess all patients who enrolled into the study via LAR to determine capacity to consent as described in the section '*Patient Participants: Determining Orientation/Emergence from PTA*' above, albeit conducted by telephone. A research staff member will arrange a time to conduct the informed consent process via telephone.

The research staff member will then send a self-addressed, stamped envelope along with two copies of the consent form, the HIPAA authorization form and a cover letter.

The cover letter will specify that, although subjects may review the consent form in advance, they should not sign or complete the forms until they have reviewed the forms with research staff at the scheduled informed consent session via telephone. At the scheduled phone contact, a research staff member will follow the informed consent procedures as described above.

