**Four-Week Completion Rule:** Post-discharge questionnaires that have been started but not completed during the first contact should be completed within 4 weeks. The questionnaire date should be the date of initial data collection. If it takes longer than 4 weeks to complete the questionnaire, data collected during the initial data collection period should be verified, and the questionnaire date should be the second date that data was collected. In the unusual case where the 2 week extension window is used to complete the questionnaire beyond the 4 week time frame, (e.g. questionnaire started January 1st, questionnaire window closes January 30th, questionnaire completed February 5th), the questionnaire date should be the date of data collection that was in the questionnaire window (January 1st in this example).

**Mailout Option:** The mailing of the questionnaire will trigger the 2 week extension to the questionnaire window. Example: if research staff mail the questionnaire July 18, 2018, and the end of the window is August 31st, research staff can then receive/collect data through September 14th.

Mailouts are exempt from the four-week extension rule listed above.

**Patient Participants Only (i.e. Not Caregiver Participants):** If adequate data are not obtained from the participant by telephone or by mailout two weeks before the end of the window, the mailout questionnaire should be sent a significant other SUBID and mailing date have been added to the form, along with a self-addressed return envelope. Like the mailing of the questionnaire to the patient participant, the mailing will trigger the 2 week extension to the questionnaire window. Example if research staff mail the questionnaire July 18, 2018, and the

end of the window is August 31st, research staff can then receive/collect data through September 14th.

Missing data may not be filled in using data obtained outside the questionnaire window and two-week extension rule unless approved by the lead site.

To classify a questionnaire as “followed” an interview or mailout must be started. There is no minimum number of data elements that need to be answered.

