Research staff will attempt to reach participants to complete these questionnaires until: 1) the questionnaire is completed, 2) the participant declines or is deemed unable to complete the questionnaire (withdrawal, death, etc.), or 3) the questionnaire window (and two-week extension rule, if applicable) expires.

Research staff may send out a letter in advance to both patient and caregiver participants reminding them of the upcoming questionnaires.

Any administrations that fall outside of the windows described above will be documented as protocol deviations using the study note-to-file form.

All follow-up data described above will be entered in with the participant's ID, i.e. not name into the NDSC centralized database via the 'Data' tab.

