### **Withdrawal/Discontinuation of Participants from Study Procedures**

There are two ways in which a participant (patient and caregiver) may cease participation in the study after being consented:

1. **WITHDRAWAL:** The patient and/or caregiver voluntarily terminates his/ her participation, and withdraws:
  - a. From the transition plan portion of the study (RTP only); or
  - b. From both the transition plan portion and the remaining outcome assessments.
2. **DISCONTINUATION:** The patient and/or caregiver are discontinued by study staff (for reasons detailed below):
  - a. From remaining treatment portion.
  - b. *The patient and caregiver are never discontinued from remaining data collection by study staff except*
    - i. *in the unlikely event that further data collection would be against their best interests in the judgment of the site PI and the study PI; or*
    - ii. *the patient participant has a new caregiver participant.*

Documentation is also necessary to capture what aspect of participation is affected (transition plan, or both transition plan and data collection) and who is ceasing participation (patient, caregiver, both).

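### A recruitment footnote withdraws one small group of randomised patients at month 1 in RTP but at month 3 in RDP; it conflicts with the withdrawal and masking sections, and its effect is unknown but probably small

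*Combined protocol and SAP*

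**What the plan says.** The rule is the triple-asterisk footnote to Patient Unable to Provide Consent, in the Recruitment section. It attaches to one branch only: the patient enters by LAR consent, has nobody to help with contacts and questionnaires, and clinical staff judge it "more likely than not that the patient participant will be able to participate on his/her own within one month following discharge". If such a patient is deemed unable after randomisation, the footnote sets the timing by arm:

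- RTP: "The TCM will withdraw the patient participant one month following discharge if randomized to RTP arm of the study".
- RDP: "Blinded staff will withdraw the patient participant three months following discharge if randomized to RDP arm of the study".

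Other sections bear on this:

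- **Withdrawal/Discontinuation of Participants from Study Procedures** separates voluntary withdrawal from discontinuation by staff. Staff may stop the treatment portion, but "The patient and caregiver are never discontinued from remaining data collection by study staff except" in two cases: further collection is against the person's best interests in the judgment of the site and study PIs, or there is a new caregiver.
- **Withdrawal from Transition Plan** asks for every effort to follow randomised participants through all later assessments.
- **Discontinuation** allows withdrawal at the PI's discretion, does not expect partial withdrawal, and ends all procedures once a participant is withdrawn.
- **Other Components of RTP** stops TCM contact attempts when a participant is deemed unable to complete them, and has the TCM record this on a plan completion form. **Documentation of Withdrawal/Discontinuation** keeps that form separate from the study completion form.
- **Questionnaire Scheduling and Timing** ends attempts at a questionnaire when "the participant declines or is deemed unable to complete the questionnaire (withdrawal, death, etc".
- **Masking (or Blinding)** requires outcome staff to be unaware of allocation.
- The **Data Analysis Plan** keeps all randomised cases in their assigned arm, imputes missing outcomes where the mechanism allows, and reports a complete-case analysis as a sensitivity analysis.

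**The concern.** The trigger for withdrawal is the same in both arms, but the date and the person who acts are not. An unblinded TCM decides at month 1 in RTP, and masked staff decide at month 3 in RDP. The 6-month primary outcome comes after both dates, and the month-1 date comes before any outcome assessment. If withdrawal ends data collection in RTP, whether a slow recoverer has a 6-month outcome depends on the arm. Randomisation does not protect against missingness created afterwards by an arm-specific rule, and an all-randomised analysis set cannot supply an outcome that was never sought. If slow recoverers participate less, the complete-case PART-O comparison moves towards RTP. For QoLIBRI, which is the patient's own rating and is not completed by proxies, the direction is less clear.

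The rule also cannot be carried out as written: masked staff would have to know that a patient is in RDP in order to apply it.

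**Working it through.** **The plan's own figures.** The documents give no number for this enrolment path, so there is no stated figure for the rule itself. The figures used as yardsticks reproduce:
- Attrition: 900 × 0.20 = 180 lost, leaving 720, or 360 per arm. With an equal split, which is assumed, 90 are lost per arm.
- Design effect: 0.4 / 0.75 = 0.5333 SD. Power at 0.5 SD with 500 patients is 0.9999, which matches the plan's practically 100%.
- At 720 patients the standard error of the difference is √(4/720) = 0.0745 SD. The effect detectable with 80% power at two-sided 0.05 is (1.960 + 0.842) × 0.0745 = 0.209 SD.

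**Assumed inputs (none is in the documents).** Let q be the share of each arm on this path, 2–10%. Let u1 and u3 be the shares of them unable at months 1 and 3, 30–50% and 10–20%. Let δ be the outcome deficit of late recoverers, 0.5–1.0 SD.

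**Reading A: in RTP, withdrawal means the whole study.** Patients still unable at month 3 are lost in both arms. Only those unable at month 1 and able by month 3 differ: RTP loses them and RDP keeps them.

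Extra RTP losses = 450 × q × (u1 − u3). Complete-case shift towards RTP = q(u1 − u3)δ / (1 − q·u3).

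| q, u1, u3, δ | Extra RTP losses | Shift (SD) | Two-sided type I error |
|---|---|---|---|
| 0.02, 0.30, 0.20, 0.5 (least adverse) | 0.9 | 0.0010 | 0.050 |
| 0.06, 0.40, 0.15, 0.75 (midpoints) | 6.75 | 0.0114 | 0.053 |
| 0.10, 0.50, 0.10, 1.0 (most adverse) | 18 | 0.0404 | 0.084 |

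The midpoint row is 0.06 × 0.25 × 0.75 / (1 − 0.009) = 0.0114 SD, or 0.0085 PART-O points at SD 0.75. If the path is only 2% of patients, the shift is at most 0.02 × 0.40 × 1 / (1 − 0.002) = 0.0080 SD.

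A second set of assumptions uses shift = path share × share unable at month 1 × share of those able by month 3 × deficit:
- 0.10 × 0.50 × 0.67 × 1 = 0.034 SD, type I error 0.073.
- Stress case with a 17% path share: 0.17 × 0.50 × 0.67 × 1 = 0.057 SD (0.043 PART-O points), type I error 0.119.

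**Reading B: in RTP, withdrawal means the TCM contacts only.** The formal loss then falls on RDP at month 3. If masked staff apply the month-3 rule to everyone they contact, the arms are treated alike and the difference is about zero. If they somehow apply it to RDP alone, let r be the share of patients unable at month 3 who would still supply a 6-month outcome in RTP, by later recovery or because "the mailout questionnaire should be sent a significant other" and it came back. Then shift = −δ·q·u3·r / (1 − q·u3(1 − r)):
- q = 0.06, u3 = 0.15, δ = 0.75, r = 0.3: −0.002 SD.
- q = 0.10, u3 = 0.20, δ = 1, r = 0.5: −0.010 SD.

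**Which reading the text supports.** For A: the Discontinuation section does not expect partial withdrawal. For B: the TCM is the actor, TCM contacts have their own stopping rule and form, and staff may stop treatment alone. RDP has no transition plan to leave, so there the word must reach data collection on either reading. The conflict with the rule on data collection therefore exists in RDP at least.

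**The case against.** The timing has a practical origin. The TCM sees RTP patients within weeks, whereas RDP patients are first contacted for outcomes at month 3. Eligibility already excludes those "unable to complete study procedures due to cognitive/verbal limitations AND do not have a proxy to assist with study procedures", so the footnote can be seen as completing that screen. Both points explain the rule. Neither removes the asymmetry, because these patients were validly enrolled and randomised. PI discretion does not cover it either, since the footnote gives the action to the TCM and to masked staff.

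Two objections limit the point. The instruction to follow randomised participants is written for people who wish to leave the transition plan, and it asks for effort, so the footnote sits against it without flatly contradicting it. And a patient with no helper who cannot answer will often have a missing questionnaire under any rule. The firm conflicts are with the rule on staff discontinuation and with masking.

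A reader might infer that RTP certainly drops these patients from the whole study at month 1, that intention to treat is abandoned, or that the primary result is materially biased towards RTP. The documents do not support this. The meaning of withdrawal in RTP is open, the analysis set remains all randomised cases, complete-case analysis is a sensitivity analysis, and recorded injury severity and discharge function may let imputation reduce any shift.

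**Conclusion.** The concern holds as a minor one. The footnote is inconsistent with the staff-discontinuation rule in RDP on any reading, and in both arms if RTP withdrawal means the whole study. Masked staff cannot apply it as written. Arm-dependent missingness follows only under the whole-study reading, and only through patients unable at month 1 and able by month 3.

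The size is unknown because the documents give no count. It is probably small: of the order of 0.01 SD, and about 0.03 to 0.06 SD under adverse assumptions, against a detectable effect of 0.209 SD and a design effect of 0.5333 SD. These figures apply to complete-case data only and rest wholly on assumed prevalence, recovery and outcome deficit. Confidence is medium.

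**What to change.** 1. Reconcile the footnote with Other Components of RTP, Questionnaire Scheduling and Timing, Masking, and the withdrawal, discontinuation and documentation sections. State whether *withdraw* means the TCM contacts or the study. Handling of the TCM contacts is for the sponsor to reconcile; no rule is proposed here.
2. Remove the arm-specific withdrawal from outcome collection. These patients stay in their assigned arm and are approached at 3, 6, 9 and 12 months under the same rule in both arms. Inability is recorded with the existing Participant Retention reason (physically or cognitively unable, no proxy available).
3. Participant Flow Tracking and the Data Analysis Plan already promise questionnaire completion in the CONSORT diagram and reasons for drop-out. Break these down by arm and timing for footnote withdrawals, using the completion forms.
4. If patients on this branch can be identified in both arms from enrolment records, add one sensitivity analysis that excludes them from both arms. Do not substitute all LAR-enrolled patients. They should be easy to find, since "Research staff will re-assess all patients who enrolled into the study via LAR to determine capacity to consent", but they include patients with helpers who were never subject to the footnote. The group could also be large: the Background says more than half of such inpatients are still in post-traumatic amnesia one month after injury.

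Cost: one wording correction, one breakdown by arm and, if feasible, one analysis; no extra patients or procedures. No section shows a data field for this branch, so item 4 may need a records check. The 12-month follow-ups were due by 10/31/2022, before version 15.0 (01-23-23), so item 2 would change practice for few or no patients. Analyses were due 7/15/2023, so at version 15.0 items 3 and 4 could still be added.

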### *Caregiver Participants*

Caregiver participants will be those individuals who will have primary care giving responsibility following rehabilitation care discharge of patients with moderate to severe TBI. Caregivers may be recruited while the patient is in the hospital or by telephone if not available during hospitalization. Research staff may enroll more than one individual as a caregiver following subject enrollment should a different individual assume the role of caregiver at a later time point (e.g. mother pre-discharge, significant other 3 months post-discharge). Multiple caregiver participants may be enrolled at the same time to accommodate if the caregiver role is assumed by different individuals at different points in time during participation (e.g. mother is caregiver at 3- and 9-months post-discharge, significant other is caregiver at 6- and 12-months post-discharge). Research staff will assess who has primary caregiving responsibilities both at each questionnaire period and the RTP phase (if applicable), and engage accordingly the particular participant who most clearly fits the role of primary caregiver.

Each site will assign a patient participant's ID number to their respective caregivers. The caregiver participant will keep the same ID number if enrolled in the study. Research staff will record which caregiver completes each questionnaire if more than one caregiver participant is enrolled at any given time.

### *Basic Demographic Information: All Potential Patient Participants*

Basic demographic information including age, sex, and race will be collected via medical record review without consent from all patients including those who do not enroll to determine differences between enrolled patients participants and those who do not enroll. These data will be entered in de-identified form into the TBIMS National Data and Statistical Center at Craig Hospital.

Screening procedures do not require a physical examination or laboratory procedures.

